9.5. Adverse Events of Special Interest

Not applicable.

9.6. Emergency Unblinding of Treatment Assignment

In a medical emergency, if knowledge of the treatment assignment is necessary to determine optimal medical management of the participant, the procedure for emergency unblinding is provided in the Pharmacy Manual. This option may be used only if the participant's well-being requires the investigator to be aware of the participant's treatment assignment. If a participant's treatment assignment must be unblinded, the sponsor must be notified immediately by telephone.

9.7. Pregnancy

Pregnancy, in and of itself, is not regarded as an AE unless there is suspicion that study treatment may have interfered with the effectiveness of a contraceptive medication or method. When a pregnancy has been confirmed in a participant during maternal or paternal exposure to study treatment, the following procedures should be followed in order to ensure safety:

- The study treatment must be discontinued immediately.
- The investigator must complete and submit the Incyte Clinical Trial Pregnancy Form to the sponsor or its designee within **24 hours** of learning of the pregnancy.

Data on fetal outcome are collected for regulatory reporting and drug safety evaluation. Follow-up should be conducted for each pregnancy to determine outcome, including spontaneous or voluntary termination, details of the birth, and the presence or absence of any birth defects, congenital abnormalities, or maternal and/or newborn complications, by following until the first well-baby visit. Pregnancy should be recorded on a Clinical Trial Pregnancy Form and reported by the investigator to the sponsor or its designee. Pregnancy follow-up information should be recorded on the same form and should include an assessment of the possible causal relationship to the sponsor's study treatment to any pregnancy outcome, as well as follow-up to the first well-baby visit or the duration specified in local regulations, whichever is later. Refer to the Incyte Reference Guide for Completing the Clinical Trial Pregnancy Form.

Any SAE occurring during pregnancy of a study participant must be recorded on the Serious Adverse Event Report Form and submitted to the sponsor or designee.

Abnormal pregnancy outcomes (eg, spontaneous abortion, fetal death, stillbirth, congenital anomalies, or ectopic pregnancy) are considered SAEs (if occurring in the study participant) and must be reported as described in Section 9.4. If an abnormal pregnancy outcome is reported in a study participant's partner, the event should be reported to the sponsor on the Clinical Trial Pregnancy Form.

9.8. Warnings and Precautions

Special warnings or precautions for the study treatment derived from safety information collected by the sponsor or its designee, are presented in the Section 2.4. Additional safety information collected between IB updates will be communicated in the form of Investigator Notifications. Any important new safety information should be discussed with the participant during the study, as necessary. If new significant risks are identified, they will be added to the ICF.

9.9. Product Complaints

The sponsor collects product complaints on itacitinib and drug delivery systems used in clinical studies in order to ensure the safety of study participants, monitor quality, and facilitate process and product improvements.

All product complaints associated with material packaged, labeled, and released by the sponsor or its designee will be reported to the sponsor. All product complaints associated with other study material will be reported directly to the respective manufacturer.

The investigator or his/her designee is responsible for reporting a complete description of the product complaint via email or other written communication to the sponsor contact or respective manufacturer as noted in the packaging information. Any AE associated with a product complaint should be recorded as described in Section 9.3.

If the investigator is asked to return the product for investigation, he/she will return a copy of the product complaint communication with the product.

9.10. Treatment of Overdose

For this study, any dose of greater than 400 mg within a 24-hour time period will be considered an overdose.

In the event of an overdose, the investigator or treating physician should:

- Contact the medical monitor immediately.
- Closely monitor the participant for any AE/SAE and laboratory abnormalities for at least 2 days.

■ [REDACTED]

■ [REDACTED]

■ [REDACTED]

- Document the quantity of the excess dose as well as the duration of the overdose in the eCRF.

Decisions regarding dose interruptions or modifications will be made by the investigator in consultation with the medical monitor based on the clinical evaluation of the participant.

10. STATISTICS

10.1. Sample Size Determination

Part 1 is a single-arm open-label study. The sample size calculation is based on the primary endpoint of \geq Grade 2 CRS rate by Day 14. It was considered that $60\% \geq$ Grade 2 CRS by Day 14 is clinically relevant in this setting. Based on a target rate of 60%, a sample size of 62 will provide 90% power to exclude a higher limit of 79% of a 2-sided 95% CI. The sample size calculation is based on an efficacy evaluable analysis set (see Section [10.2](#) for definition).

[Table 18](#) represents CRS Rates and CIs for a sample size of 62.

Table 18: CRS Rates and 95% Confidence Intervals

Sample Size	Number of CRS	CRS Rate (%)	95% Confidence Interval (%)
62	36	58.1	44.8, 70.5
62	38	61.3	48.1, 73.4
62	40	64.5	51.3, 76.3
62	42	67.7	54.7, 79.1
62	44	71.0	58.1, 81.8

Part 2 is a randomized expansion of the study; itacitinib 200 mg BID versus placebo.

As in Part 1, the primary endpoint is Grade \geq 2 CRS rate by Day 14. Assuming Grade \geq 2 CRS rate in the placebo arm is 50% ([Nastoupil et al 2020](#)) and a 20% in the treatment arm (~30% change in CRS rate), a sample size of 23 evaluable participants per group would provide 70% power based on a 1-sided Type-I error rate of 5%. Sufficient number of participants will be enrolled to yield 23 evaluable participants in each group.

A Bayesian interpretation for the selection and impact of the sample size can be provided in terms posterior probabilities. As the response rate based on CRS grade has a binomial (n, p) distribution with s number of responders out of n participants, it is common to use a conjugate Beta (a, b) prior which will lead to a Beta(a + s, b + n - s) posterior distribution. For this exercise, we will assume a noninformative Beta(1,1) (~ Uniform(0,1) prior).

[Table 19](#) presents scenarios of Bayesian posterior probability of demonstrating a treatment difference ($\geq 30\%$) by Day 14 in response rates, between the itacitinib 200 mg BID group and the placebo group, under various response rates (number and percentage of responders).

Table 19: Bayesian Posterior Probability of Demonstrating a Treatment Difference

N ^a (%) 200 BID Group	N ^b (%) Placebo	Posterior Probability ^c
2 (8.7)	9 (39.1)	43.7
	12 (52.5)	79.4
	14 (60.9)	93.4
5 (21.7)	9 (39.1)	13.9
	12 (52.5)	45.9
	14 (60.9)	67.9
7 (30.4)	9 (39.1)	4.7
	12 (52.5)	22.7
	14 (60.9)	44.7

^a Number of participants with CRS \geq Grade 2, out of 23 participants, in the 200 mg BID group.

^b Number of participants with CRS \geq Grade 2, out of 23 participants, in the placebo group.

^c Bayesian posterior probability that the itacitinib group has at least 30% improvement over placebo, based on CRS \geq Grade 2.

Based on the scenarios presented in [Table 19](#), if we assume observed CRS rates (CRS \geq Grade 2) of 2/23 (8.7%) and 12/23 (52.2%) in the itacitinib and placebo groups, respectively, then a Bayesian calculation is expected to yield a posterior probability of 79.4% of seeing an increase of at least 30% in the placebo group.

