As of the preplanned interim analysis data cutoff (08 JAN 2021), 26 participants were enrolled, 25 participants had completed Day 28 (EOT visit), and 26 participants had completed Day 14. The primary intent of this analysis was to minimize unnecessary exposure to itacitinib in the event of futility of preventing CRS. Of the 26 participants, 3 (11.5%) participants experienced CRS Grade 2, and there was no participant with \geq Grade 3 CRS. Two participants received tocilizumab for CRS Grade 1. Five (19.2%) participants had \geq Grade 2 ICANS. Results from this interim analysis have shown itacitinib to be well-tolerated, with preliminary evidence of clinical activity for the prevention of CRS and ICANS.

A PK analysis was also performed, based on the interim data cutoff described above. Exposures were generally similar in this patient population to those observed in other patient populations receiving the same dose at steady state, 200 mg QD. The exposure range for itacitinib when dosed with axicabtagen ciloleucel or tisagenlecleucel are highly overlapping, although limited patients had received tisagenlecleucel. At the time of this interim analysis there was no apparent

[figure not shown]
exposure/response relationship between measures of exposure (ie, AUC, C_{max} , and C_{min}) and CRS or ICANS grade.

2.3.4. Rationale for Part 2

An additional dosing regimen of itacitinib will be explored in an expanded, Part 2, of the study based on the following rationale:

- Although preliminary data from Part 1 are promising, target coverage following 200 mg QD is < 10 hours, suggesting BID dosing may offer greater target coverage over 24 hours.

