An interim analysis for CRS futility will be conducted when 24 participants are treated with IEC therapy, in Part 1, and complete the Day 28 (EOT) visit. The study may be stopped for futility at the interim analysis if the conditional power based on interim results is lower than 20%, which is equivalent to more than 17 out of 24 participants experiencing \geq Grade 2 CRS by Day 14.

See Section 6.1 for full itacitinib administration information and to [Table 3](#), Schedule of Assessments in Section 1, Protocol Summary. Decentralized assessments are acceptable; however, principal investigator oversight is required.

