10.3. Level of Significance

Part 1: There is no formal hypothesis testing in this study. CRS rate as well as associated 95% exact CI by Clopper-Pearson method will be provided ([Clopper and Pearson 1934](#)).

Part 2: For the efficacy endpoints subjected to hypothesis testing, the 1-sided Type I error will be controlled at 0.05 for each individual cohort expansion. For other endpoints, CIs will be reported at a 95% confidence level.

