3.3. Control of Type I Error

For Part 1, analysis of CRS rate, 2-sided 95% exact confidence level by Clopper-Pearson method will be reported ([Clopper and Pearson 1934](#)).

For Part 2, the analysis of the primary efficacy endpoint, a 2-sample t test with 1-sided Type I error of 0.05 will be conducted to test the difference between the 2 treatment groups. Two-sided 95% CIs will be reported, for the primary efficacy endpoint for each treatment group and the difference between the 2 treatment groups.

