7.2. Analysis of the Primary Efficacy Parameter

7.2.1. Primary Efficacy Analysis

The primary endpoint of the study is CRS rate by Day 14, defined as the percentage of participants experiencing \geq Grade 2 CRS by Day 14 after IEC therapy.

In Part 1, the CRS rate will be calculated for each treatment group as follows:

$$\text{CRS rate} = \frac{x}{n}$$

where n is the number of efficacy evaluable participants, and x is the number of efficacy evaluable participants who experience \geq Grade 2 CRS by Day 14.

The exact 95% CI (2-sided) will be calculated using the Clopper-Pearson method ([Clopper and Pearson 1934](#)), as the following:

$$(B\left(\frac{\alpha}{2}; x, n - x + 1\right), B(1 - \frac{\alpha}{2}; x + 1, n - x))$$

where $B(p; v, w)$ is the p th percentile from a beta distribution with shape parameters v and w , and α is 5%.

In Part 2, the CRS rate and the associated 95% CI will also be calculated for each treatment group, itacitinib 200 mg BID and placebo, in the same way as the analysis for Part 1. The primary efficacy endpoint analysis will be the comparison of the percentage of efficacy evaluable participants experiencing \geq Grade 2 CRS by Day 14 between the 2 treatment groups. The CRS rates will be compared using a 1-sided Z-test at the significance level of 0.05, and a 95% CI (2-sided) for the difference in the CRS rate will be calculated. The following statistical hypothesis will be tested for the primary efficacy endpoint analysis:

$$H_0: \text{CRS}_A \geq \text{CRS}_B \text{ versus } H_1: \text{CRS}_A < \text{CRS}_B$$

where CRS_A and CRS_B will be the CRS rates for itacitinib 200 mg BID and placebo, respectively. The Z-test for the difference between the 2 treatment groups will be based on the following test statistic:

$$z = \frac{\widehat{\text{CRS}}_A - \widehat{\text{CRS}}_B}{\sqrt{\widehat{\text{CRS}}(1 - \widehat{\text{CRS}})\left(\frac{1}{n_1} + \frac{1}{n_2}\right)}}$$

where n_1 and n_2 are the numbers of efficacy evaluable participants for itacitinib 200 mg BID and placebo, respectively, and

$$\begin{aligned}\widehat{CRS}_A &= \frac{x_1}{n_1} \\ \widehat{CRS}_B &= \frac{x_2}{n_2} \\ \widehat{CRS} &= \frac{x_1 + x_2}{n_1 + n_2}\end{aligned}$$

where x_1 and x_2 are the number of efficacy evaluable participants experiencing CRS \geq Grade 2 by Day 14 for the treatment group, itacitinib 200 mg BID and placebo, respectively.

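### Part 1's stated 90% power to exclude a 79% CRS rate is 86.8% under the exact Clopper-Pearson interval that the plan will report

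*Protocol*

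**What the plan says.** Protocol 10.1 sizes Part 1 on the primary endpoint, the proportion with Grade 2 or higher CRS by Day 14. "Based on a target rate of 60"%, it states that "a sample size of 62 will provide 90% power to exclude a higher limit of 79% of a 2-sided 95% CI". SAP 3.4 carries the same sentence. The 62 are evaluable participants: "The sample size calculation is based on an efficacy evaluable analysis set". Neither document says how the 90% was calculated.

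Both documents do name the interval. Protocol 10.3 says of Part 1 that "CRS rate as well as associated 95% exact CI by Clopper-Pearson method will be provided". SAP 3.3 says that a "2-sided 95% exact confidence level by Clopper-Pearson method will be reported", and SAP 7.2.1 repeats it and gives the beta-quantile formula: "The exact 95% CI (2-sided) will be calculated using the Clopper-Pearson method". Protocol Table 18 and SAP Table 2, printed below the power sentence, list intervals for 36, 38, 40, 42 and 44 events out of 62. The 42/62 row reads 54.7 to 79.1.

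Protocol 10.3 also says that Part 1 involves no formal hypothesis test.

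**The concern.** The power sentence describes a property of a confidence interval: how often its upper limit will fall below 79% if the true rate is 60%. The plan commits to one interval for Part 1, so the figure should hold for that interval.

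The table under the sentence suggests that it does not. At 42 of 62 the printed upper limit is 79.1, which does not exclude 79%. The table has no row for 41, so the reader cannot see where the boundary falls, and the probability attached to the boundary count decides whether 90% is right.

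What is at stake is an accurate description of the design. The same figure stands in two governing documents and could be carried into the study report, where a reader could refute it from the adjacent table.

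**Working it through.** **Inputs.** n = 62, true rate p1 = 0.60, limit to exclude p0 = 0.79, two-sided 95% (Protocol 10.1, SAP 3.4). Interval: Clopper-Pearson (Protocol 10.3, SAP 3.3 and 7.2.1). No dropout allowance enters, since the 62 are evaluable participants.

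**Step 1: can the plan's 90% be reproduced?** Let d = 0.79 − 0.60 = 0.19, se0 = √(0.79 × 0.21/62) = 0.0517 and se1 = √(0.60 × 0.40/62) = 0.0622.

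- Normal with continuity correction: Φ[(d − 1/(2n) − 1.96·se0)/se1] = Φ[(0.19 − 0.0081 − 0.1014)/0.0622] = 90.2%.
- Arcsine: Φ[(2·arcsin√0.79 − 2·arcsin√0.60)·√62 − 1.96] = 90.8%.
- Normal without correction, null variance for the critical value and alternative variance for power: 92.3%.
- Wald form, alternative variance throughout: 86.3%.

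The stated figure is therefore recognisable from at least two standard formulas.

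**Step 2: the planned interval.** The Clopper-Pearson upper limit for x events is the 0.975 quantile of Beta(x + 1, n − x). All five printed rows reproduce. Around the boundary:

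| Events of 62 | Rate (%) | Exact 95% CI (%) | Upper limit below 79%? |
|---|---|---|---|
| 40 | 64.5 | 51.34, 76.26 | yes |
| 41 | 66.1 | 52.99, 77.67 | yes |
| 42 | 67.7 | 54.66, 79.06 | no |
| 43 | 69.4 | 56.35, 80.44 | no |

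Equivalently, 79% is excluded when P(X ≤ x | 62, 0.79) is below 0.025. That probability is 0.0129 at x = 41 and 0.0257 at x = 42. The largest qualifying count is 41.

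**Step 3: power under that interval.** P(X ≤ 41 | 62, 0.60) = 0.8681, or 86.8%. The shortfall is 90 − 86.8 = 3.2 points. If 42 also counted, P(X ≤ 42 | 62, 0.60) = 0.9168, or 91.7%.

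**Step 4: other intervals, by exact binomial enumeration.** Wilson, Agresti-Coull, Jeffreys and mid-P intervals all admit 42/62 and give 91.7%. The Wald interval, like Clopper-Pearson, stops at 41/62 and gives 86.8%.

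**Step 5: how far this is a matter of discreteness.** Exact Clopper-Pearson power is 90.1% at n = 61, 86.8% at 62, 88.8% at 63 and 90.5% at 64. The dip at 62 is a step in a sawtooth.

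**The case against.** The strongest reply is that 90% is a reasonable planning figure. Two common approximations give it, and exact power is 91.7% with several respectable intervals. The limit is written as a whole percentage, and 79.06% is 79% at that precision. Read so, 42/62 qualifies and even Clopper-Pearson power is 91.7%. Part 1 is descriptive, so nothing is decided by the count of 41 or 42.

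Much of this stands. The 90% need not be a slip of calculation, and the difference rests on 0.06 points at one count. But the tables report to one decimal and print 79.1, which is above 79, and the exact tail probability of 0.0257 exceeds 0.025. The strict reading is the one the documents' own table supports. The methods that reach 90% are not the one the plan commits to.

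Three stronger readings are tempting and are not supported:

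- A reader might infer that 90% holds only by normal approximation. Some normal approximations miss it (86.3% for the Wald form), while Jeffreys and mid-P intervals with exact binomial power give 91.7%. No method is named, so the origin of the 90% cannot be established.
- A reader might infer that the futility boundary in Protocol 10.5 and SAP 10 conflicts with the count of 41. The visible text gives no conditional-power method, text beside the rule is redacted, and whether the boundary fits 41 or 42 depends on the method assumed. The boundary was also to be re-evaluated at the interim, which has taken place. No inconsistency can be claimed.
- A reader might infer that Part 1 is too small. One participant fewer would give 90.1%, and no test depends on the figure.

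**Conclusion.** The power sentence is inaccurate for the interval the plan will report: 86.8% against a stated 90%. This assumes a true rate of 60%, exactly 62 evaluable participants, and 79% read as 79.0%. If 79.06% is accepted as 79%, the figure is 91.7% and the sentence is met.

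The practical effect is minor. Part 1 has no formal test, the printed intervals are correct, and the result against 79% appears settled in any case. Protocol 2.3.3 reports at the interim: "Of the 26 participants, 3 (11.5%) participants experienced CRS Grade 2", with none at Grade 3 or higher and all 26 past Day 14. If those 26 are in the evaluable set, their counts stand, and every one of the remaining 62 − 26 = 36 had an event, the total would be 3 + 36 = 39 of 62, with an upper limit of 74.8%. What remains is a correction to the record.

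**What to change.** Keep N = 62 and the 79% limit. In Protocol 10.1 and SAP 3.4, restate the sentence along these lines: with 62 evaluable participants and a true rate of 60%, the probability that the upper limit of the exact two-sided 95% Clopper-Pearson interval lies below 79% is about 87% (86.8%), which requires 41 or fewer events. If the 90% is kept alongside, name the approximation that produces it. A 41/62 row (66.1%; 53.0, 77.7) in Protocol Table 18 and SAP Table 2 would show the boundary, but is optional.

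The cost is one sentence in each document. Sample size, futility rule, analysis and conduct do not change.

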10.2. Populations for Analysis

[Table 20](#) presents the populations for analysis.

Table 20: Populations for Analysis

Population	Description
Safety population	The safety population includes all enrolled participants who received at least 1 dose of study treatment. All safety analyses will be conducted using the safety population.
Efficacy evaluable analysis set (EAS)	The EAS includes all participants who have received at least 1 dose of study treatment and have received IEC therapy. All efficacy analyses will be conducted using EAS.

10.3. Level of Significance

Part 1: There is no formal hypothesis testing in this study. CRS rate as well as associated 95% exact CI by Clopper-Pearson method will be provided ([Clopper and Pearson 1934](#)).

Part 2: For the efficacy endpoints subjected to hypothesis testing, the 1-sided Type I error will be controlled at 0.05 for each individual cohort expansion. For other endpoints, CIs will be reported at a 95% confidence level.

10.4. Statistical Analyses

The Statistical Analysis Plan will be developed and finalized before database lock and will describe the participant populations to be included in the analyses and procedures for accounting for missing, unused, and spurious data. This section is a summary of the planned statistical analyses of the primary and secondary endpoints. Analysis will be summarized by IEC therapy and overall population in both efficacy and safety analysis.

10.4.1. Primary Analysis

10.4.1.1. CRS Rate by Day 14

The primary endpoint of the study is CRS rate by Day 14, defined as the percentage of participants experiencing \geq Grade 2 CRS by Day 14. The primary analysis of CRS rate will be based on the EAS in overall population. CRS rate and its exact 95% CI will be presented. In addition, CRS rate will be provided separately for each IEC therapy.

10.4.1.2. Cytokine Release Syndrome Rate by Day 14 – Part 2

The primary endpoint of the study is CRS rate by Day 14, defined as the percentage of participants experiencing \geq Grade 2 CRS by Day 14. The primary analysis of CRS rate will be based on the EAS in overall population. The primary hypothesis to be tested is to compare itacitinib 200 BID versus placebo. CRS rates will be compared using a 1-sided ($\alpha=0.05$) test and will be complemented by a 95% CI.

As sensitivity and supportive analysis, Bayesian posterior probabilities of crossing various thresholds of improvements over placebo (eg, 30%), as well as credible intervals will be computed using a noninformative Uniform (0,1) prior.

10.4.2. Secondary Analysis

10.4.2.1. Part 2 Analysis

The secondary analysis in Part 2 will be conducted by first comparing the itacitinib 200 mg QD dose from Part 1 with the placebo group in Part 2, using a 95% CI. This comparison will include participants who were treated with Yescarta, thus ensuring similarity in the underlying population. A sensitivity analysis will also be conducted as an empirical comparison between treatment groups.

Comparisons between treatment groups will be done at the summary level, based on rates and CIs, which will add to the determination of the optimal dose and schedule of itacitinib for subsequent trials. Pairwise Cochran-Mantel-Haenszel tests and trend tests (eg,

Final dose selection will include results from these tests as well as from other endpoints including safety, rescue medication required

Similar comparisons between the treatment groups and placebo will also be conducted for other secondary endpoints explored in Part 1, as explained in sections below. Evidence from these comparisons will also be used in selecting the optimal dose and schedule of itacitinib for subsequent trials.

